DPS	Data programming specifications
EBOV GP	Ebola virus (formerly known as Zaire ebolavirus) Mayinga glycoprotein
eCRF	Electronic case report form
ELISA	Enzyme-linked immunosorbent assay
EU/mL	Elisa units/mL
FAS	Full analysis set
FDA	Food and Drug Administration
IRE	Immediate Reportable Event
LLOQ	Lower limit of quantification
MeDRA	Medical Dictionary of Regulatory Activities
NSAIDs	Non-steroidal anti-inflammatory drugs
PP	Per protocol
PRNT	Plaque reduction neutralization test
SAE	Serious adverse event
SAP	Statistical analysis plan
SD	Standard deviation
ULOQ	Upper limit of quantification
VNA	Virus neutralization assay
WHO	World Health Organization

1. INTRODUCTION

This is the statistical analysis plan (SAP) for the phase 2 VAC52150EBL2011 study. This SAP will be applicable to the study results based on version 2.0 of the clinical protocol of 15 June 2021.

1.1. Trial Objectives

The primary objectives of the study are:

- To assess the safety and tolerability of a booster dose of Ad26.ZEBOV at a dose of 5×10^{10} viral particles (vp) in children previously vaccinated with Ad26.ZEBOV, MVA-BN-Filo vaccine regimen with a 56-day interval.
- To assess the vaccine-induced humoral immune response to the Ebola virus glycoprotein (EBOV GP), as measured by FANG ELISA, at 7 and 21 days following a booster dose of Ad26.ZEBOV at a dose of 5×10^{10} vp in children previously vaccinated with Ad26.ZEBOV, MVA-BN-Filo vaccine regimen with a 56 day interval.

1.2. Trial Design

This is a phase 2 open label study to evaluate the immune response to a booster dose of Ad26.ZEBOV administered to children who were previously vaccinated with Ad26.ZEBOV followed by MVA-BN-Filo 56 days later. Only children who received Ad26.ZEBOV and MVA-BN-Filo regimen during their participation in VAC52150EBL3001 (EBOVAC-Salone) vaccine trial are eligible for enrolment in this study. Participants will be recruited in two age groups: children aged 4-11 years at the time of dose 1 vaccination and children aged 1-3 years at the time of dose 1 vaccination in the EBOVAC-Salone trial. Approximately 25 participants will be enrolled in each of these two age groups.

Participants will be followed up to 28 days after their booster vaccination.

1.3. Statistical Hypotheses for Trial Objectives

As this study is designed to provide descriptive information regarding safety and immunogenicity without formal treatment comparisons, no formal statistical hypothesis testing is planned.

1.4. Sample Size Justification

Approximately 50 participants are expected to be enrolled in this trial (approximately 25 for each age group). The sample size is a convenience sample and is not based on formal hypothesis testing considerations.

1.5. Randomization and Blinding

Randomisation

There will be no randomisation in this study with all participants receiving the booster dose of Ad26.ZEBOV vaccine.

Blinding

This is an open label study in which all the participants will receive the booster dose of Ad26.ZEBOV vaccine.

2. GENERAL ANALYSIS DEFINITIONS

Data will be shown by the study age groups (1-3 and 4-11 years). A booster baseline (or reference) value will be described as the value of the last available assessment performed prior to booster vaccination on Day 1.

Unless otherwise specified, the results of the statistical analysis will be presented by period, except for participant information sections. For immunogenicity, vital signs, and physical examination, data will be presented per time point as appropriate. Assessments over time will be reported for each period or visit (see Section 2.1).

- Categorical variables will be summarised using the following statistics: number of observations, percentages and Exact Clopper-Pearson 95% confidence interval (CI), as applicable.
- Continuous variables will be summarised using the following statistics as appropriate: number of observations, geometric mean, arithmetic mean (mean), 95% confidence interval (CI) for the mean, standard deviation (SD), standard error (SE), median, quartiles (Q1 and Q3), minimum and maximum. In addition, reverse cumulative distribution plots will be used for exploratory analysis of antibody data.

Unless otherwise specified, listings will only be generated for final analysis.

2.2. Pooling of Data

Results will be pooled over sites.

2.3. Analysis Sets

2.3.1. Full Analysis Set

The full analysis set will include all participants with the study intervention administration documented. All safety analysis will be performed on the full analysis set. In case a significant number of subjects are excluded from per protocol set ($\geq 10\%$), then the immunogenicity analysis conducted on the full analysis set will be presented as sensitivity analysis, to investigate the impact of major protocol deviations on immune response.

2.3.2. Per Protocol Immunogenicity Population

The per-protocol immunogenicity population will include all vaccinated participants for whom immunogenicity data are available, excluding participants with major protocol deviations expected to impact the immunogenicity outcomes. The primary immunogenicity analysis will be performed on the per protocol immunogenicity population.

2.4. Definition of Subgroups

Data will be shown by age groups (1-3 years and 4-11 years).

These subgroups will be used for showing the data for both safety analysis (full analysis set) and immunogenicity analysis (per protocol immunogenicity population).

3. CHANGES TO THE PLANNED ANALYSIS

No changes have been made to the planned analysis contained in the protocol.

INTERIM ANALYSIS AND DATA MONITORING COMMITTEE REVIEW

No interim analysis will be performed for this study.

An IDMC will not be appointed for this study. The safety of Ad26.ZEBOV has already been shown in children in previous studies. A booster dose of Ad26.ZEBOV was also shown to be safe in adults. Thus the role of the IDMC will be designated to an independent medical reviewer. The independent medical reviewer will be identified by the sponsor to review the accumulating safety data on an ongoing basis to ensure the continuing safety of the participants enrolled in this study.

The independent medical reviewer will be consulted periodically to review newly generated data. Ad hoc meetings may be requested via the sponsor if any of the pre-specified pausing rules for this study are met or in any situation that could affect the safety of the participants.

For more details, refer to section 10.7 of the protocol.⁽¹⁾

4. PARTICIPANT INFORMATION

Participant information will be analysed based on the full analysis set.

4.1. Demographics and Baseline Characteristics

Demographic characteristics and screening/baseline characteristics (e.g. physical examination, medical history) will be tabulated and summarized with descriptive statistics.

The following demographic and baseline characteristics will be summarized:

- Sex (Male/ Female)
- Age (years)
- Race
- Ethnicity
- Height
- Weight
- Weight-for-age for children 2-5 years and 5-10 years according to WHO growing charts
- Height-for-age for children 2-5 years and 5-19 years according to WHO growing charts
- Weight-for-height for children 2-5 years according to WHO growing charts
- BMI-for-age for children 5-19 years according to WHO growing charts
- Time between vaccination with Ad26.ZEBOV/ MVA-BA-Filo regimen and Ad26.ZEBOV booster vaccination (Median time, Q1, Q3, and range)

The charts are available from the link below:

<https://www.who.int/tools/child-growth-standards/standards/weight-for-age>

<https://www.who.int/tools/growth-reference-data-for-5to19-years/indicators/weight-for-age-5to10-years>

<https://www.who.int/tools/child-growth-standards/standards/length-height-for-age>

<https://www.who.int/tools/growth-reference-data-for-5to19-years/indicators/height-for-age>

<https://www.who.int/tools/child-growth-standards/standards/weight-for-length-height>

<https://www.who.int/tools/growth-reference-data-for-5to19-years/indicators/bmi-for-age>

4.1.1. Description of the procedure to determine Weight-for-Age percentile

Reference material in Excel format can be found at this link for boys and girls:

[https://www.who.int/docs/default-source/child-growth/growth-reference-5-19-years/weight-for-age-\(5-10-years\)/wfa-girls-perc-who2007-exp.xlsx?sfvrsn=5c5825c4_4](https://www.who.int/docs/default-source/child-growth/growth-reference-5-19-years/weight-for-age-(5-10-years)/wfa-girls-perc-who2007-exp.xlsx?sfvrsn=5c5825c4_4)

[https://www.who.int/docs/default-source/child-growth/growth-reference-5-19-years/weight-for-age-\(5-10-years\)/wfa-boys-perc-who2007-exp.xlsx?sfvrsn=97ab852c_4](https://www.who.int/docs/default-source/child-growth/growth-reference-5-19-years/weight-for-age-(5-10-years)/wfa-boys-perc-who2007-exp.xlsx?sfvrsn=97ab852c_4)

Consult <https://www.who.int/growthref/computation.pdf> for more information on the data contained in the Excel file and instructions on how to calculate the exact percentile.

First determine the age point to use. Age at the date of the corresponding weight assessments is to be used. Age is to be used at the half month point for the entire month; for example, 1.5 months represents 1.0-1.99 months or 1.0 month up to but not including 2.0 months of age. Using the appropriate chart (boys vs. girls), determine the values of L, M, and S to use.

4.2. Disposition Information

The number and percentage of participants screened, vaccinated and included in each analysis set will be tabulated.

Number and percentage of participants in the full analysis set that complete the study and those who are going to be discontinued together with reasons for discontinuation will be tabulated.

4.3. Protocol Deviations

All major protocol deviations will be tabulated by deviation category. Major protocol deviations that may have an influence on immune response will be flagged in a listing.

4.4. Medical History

Medical history will be listed.

4.5. Concomitant Medications

The analysis of concomitant therapies will be done using generic drug names.

Based on their start and stop date, concomitant therapies will be reported in each analysis period during which they were applied. For missing or partial start and/or stop dates (time and/or day and/or month and/or year) the following allocation rules will be applied:

- In case of partial start or stop dates, the concomitant therapy records will be allocated to periods using the available partial information, without imputations. If, for example, only month and year are available this will be compared to the month and the year of the periods, and concomitant therapy will be allocated to the period(s) where these date parts match.
- In case of a completely missing start date, the concomitant therapy will be considered as having started before the trial.
- In case of a completely missing end date, the concomitant therapy will be considered as ongoing at the end of the trial.

Concomitant therapies will be tabulated per period (including follow up periods). A listing of all concomitant therapies will be provided. All therapies taken within 30 days prior to signing the informed consent form will also be listed.

There will be special attention to analgesics/ antipyretics such as acetaminophen, non-steroidal anti-inflammatory drugs (NSAIDS) and aspirin, administered until day 8 post-vaccination (including day of vaccination).

Remarks:

In addition to the date information, time information is considered to allocate concomitant therapies to periods, if available.

5. IMMUNOGENICITY

The primary analysis of immunogenicity will be done on the per protocol immunogenicity population (as defined in section 2.3).

5.1. Immunogenicity against EBOV GP

5.1.1. Humoral Immune response

5.1.1.1. Parameters

Humoral immune response as measured by the following assays will be analysed.

- **Binding antibody responses using Filovirus Animal Nonclinical Group (FANG) enzyme-linked immunosorbent assay (ELISA):** Quantification of antibodies binding to EBOV GP using ELISA units/mL (EU/mL).

In addition, the following will be defined for ELISA (EU/mL):

- **Sample interpretation:** a sample will be considered positive, if the value is above the assay-specific lower limit of quantification (LLOQ).
- **Responder:**
 - If sample interpretation is negative at baseline before dose 1 vaccination in EBL3001 but positive post-baseline and the post-baseline value is greater than $2.5 \times \text{LLOQ}$; OR
 - If sample interpretation is positive at both baseline before dose 1 vaccination in EBL3001 and post-baseline and there is a greater than 2.5-fold increase from baseline (2.5-fold increase on the original scale)

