Solicited local (at the administration site) and systemic AEs will be assessed on the day of vaccination and using a diary for a period of seven days following the booster vaccination. Unsolicited AEs will be tracked for 28 days following booster vaccination, while serious adverse events will be tracked for the duration of the study.

IMMUNOGENICITY EVALUATIONS

Blood will be drawn for assessments of immune responses at the time points indicated in the TIME AND EVENTS SCHEDULE. The site staff will perform sample collection and processing according to current versions of approved standard operating procedures.

Future scientific research may be conducted to further investigate Ebola vaccine- and disease-related questions and to study other infections of public health importance in Sierra Leone and neighbouring countries. This may include the development of new, or the improvement of, existing techniques to characterize EBOV-directed immune responses or diagnostic tests. No additional samples will be taken for these analyses, however, residual samples from the study tests may be retained for these purposes and analysed after the end of the study.

STATISTICAL METHODS

The primary analysis will be done when all subjects have completed their 28-day post-booster visit or discontinued earlier. This analysis will include all available data up to this point.

Sample Size Determination

The sample size is a convenience sample and is not based on formal hypothesis testing considerations.

SAFETY ANALYSES

No formal statistical testing of safety data is planned. Safety data will be analysed descriptively by age group, 1-3 years and 4-11 years (age the participant was when they received dose 1 vaccination in the EBOVAC-Salone trial).

IMMUNOGENICITY ANALYSES

No formal hypothesis on immunogenicity will be tested. Descriptive statistics (i.e. geometric mean and 95% confidence interval, as appropriate) will be calculated for continuous immunologic parameters at all available time points (i.e. Day 1, 8 and 22). Graphical representations of immunologic parameters will be made as applicable.

Frequency tabulations will be calculated for discrete (qualitative) immunologic parameters (i.e. responder rate), as applicable. Responders rate defined as >2.5-time increase over baseline value (or lower limit of quantitation [LLOQ]) pre-dose 1 vaccination in the EBOVAC-Salone trial, will be calculated depending on availability of sample results from the EBOVAC-Salone trial.

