Safety and immunogenicity of an Ad26.ZEBOV booster dose in adult participants

An Ad26.ZEBOV booster vaccination was given to 29 adult participants, who were vaccinated approximately 2 years before with Ad26.ZEBOV followed by MVA-BN-Filo 56 days later in the VAC52150EBL3001 (EBOVAC-Salone) trial in Sierra Leone. The booster vaccination was safe and induced a strong anamnestic response in 96% of participants at seven days post-booster vaccination and in all 29 participants at 21 days post-booster vaccination. [6]

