10.5 IMMUNOGENICITY ANALYSIS

No formal hypothesis on immunogenicity will be tested. Descriptive statistics (e.g. geometric mean and 95% CI) will be calculated for continuous immunologic parameters at all available time points. Graphical representations of immunological parameters will be made as applicable. Frequency tabulations will be calculated for discrete (qualitative) immunologic parameters (i.e. responder rate), as applicable. Responders rate defined as >2.5-time increase over baseline value (or LLOQ) pre-dose 1 vaccination in the EBOVAC-Salone trial, will be calculated depending on availability of sample results from the EBOVAC-Salone trial.

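### The only responder rate is measured against the sample before dose 1 in EBL3001, so no planned figure gives the proportion of children who responded to the booster

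*SAP*

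**What the plan says.** SAP 1.1 sets the immunogenicity objective as the response "at 7 and 21 days following a booster dose of Ad26.ZEBOV". SAP 2 defines a booster baseline as the "value of the last available assessment performed prior to booster vaccination on Day 1".

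The responder definition in SAP 5.1.1.1 does not use that baseline. Its first branch requires a sample that is "negative at baseline before dose 1 vaccination in EBL3001 but positive post-baseline and the post-baseline value is greater than" 2.5 x LLOQ. Its second branch requires a more than 2.5-fold rise over a positive value from the same pre-dose-1 sample. Protocol 10.5 uses the same reference: "Responders rate defined as >2.5-time increase over baseline value (or LLOQ) pre-dose 1 vaccination in the EBOVAC-Salone trial". It makes the calculation conditional, "depending on availability of sample results from the EBOVAC-Salone trial". The protocol synopsis (Immunogenicity Analyses) repeats both points. Neither document contains a second responder rule.

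SAP 5.3 plans ELISA geometric mean concentrations, fold increase from the pre-booster value at Days 8 and 22, summary statistics at Days 1, 8 and 22, reverse cumulative distribution plots, and the percentage of responders at time points it does not list. No threshold is placed on the pre-booster fold increase.

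**The concern.** The reference sample predates the whole primary regimen, so the Day 8 and Day 22 percentages combine antibody left from that regimen with any response to the booster. They show whether a child is above the unvaccinated state, not whether the child responded to the booster.

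Residual antibody is a real possibility. Protocol 1.1 reports that responses in children persisted for at least 12 months and were higher at ages 1-3 years than in the older cohorts. The synopsis puts the booster more than 2 years after the regimen and says durability is unknown. If persistence differs by age, the residual part would also differ between the two reported age groups.

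Readers are likely to take the figure as a booster response rate, because the protocol describes the adult booster that way. Protocol 1.1 says it "induced a strong anamnestic response in 96% of participants at seven days post-booster vaccination and in all 29 participants at 21 days" after the booster, without giving the rule behind those figures.

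**Working it through.** The plan has no figure of its own to reproduce: the sample is one of convenience and the study is descriptive.

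**What follows from the text.** Take a child below LLOQ before dose 1 whose Day 1 value is 4 x LLOQ and does not change. At Days 8 and 22 the value is positive and above 2.5 x LLOQ, so the child is a responder, with a fold increase from Day 1 of 1. The second branch behaves in the same way for a child already above 2.5 times a positive pre-dose-1 value.

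**Inputs for the size, all assumed.** Pre-dose-1 values are at or below LLOQ. Day 1 values are lognormal with geometric mean *k* x LLOQ and log10 SD *s1* = 0.4 (range 0.3-0.5). The individual fold rise has geometric mean *f* and log10 SD *s2* = 0.3 (range 0.2-0.4), independent of Day 1. The ULOQ is *U* x LLOQ. The 2.5 threshold and the LLOQ and ULOQ substitutions come from SAP 5.1.1.1 and 5.1.1.2.

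**Step 1: planned rule, no individual changes after the booster.** P = Φ((log10 *k* − log10 2.5)/*s1*), with log10 2.5 = 0.398. For *k* = 10 and *s1* = 0.4: Φ((1 − 0.398)/0.4) = Φ(1.505) = 0.934.

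| *k* | *s1* = 0.3 | *s1* = 0.4 | *s1* = 0.5 |
|---|---|---|---|
| 1 | 9% | 16% | 21% |
| 3 | 60% | 58% | 56% |
| 5 | 84% | 77% | 73% |
| 10 | 98% | 93% | 89% |
| 20 | 99.9% | 99% | 96% |

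**Step 2: how well each rule separates an inert booster (*f* = 1) from a 10-fold one.** Values now also vary between visits, so the inert rates differ from step 1. Planned rule: P = Φ((log10(*kf*) − log10 2.5)/√(*s1*² + *s2*²)), with √(0.16 + 0.09) = 0.5. A rule referenced to Day 1 is integrated numerically over the Day 1 distribution, with Day 1 values below LLOQ set to LLOQ. The Day 1 columns below have no ULOQ cap.

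| *k* | Planned, *f* = 1 v 10 | Gap (points) | Day 1 rule, *f* = 1 v 10 | Gap (points) |
|---|---|---|---|---|
| 1 | 21.3% v 88.6% | 67 | 5.8% v 87.7% | 82 |
| 3 | 56.3% v 98.5% | 42 | 8.6% v 96.6% | 88 |
| 5 | 72.6% v 99.5% | 27 | 9.0% v 97.5% | 88 |
| 10 | 88.6% v 99.9% | 11 | 9.2% v 97.7% | 89 |
| 20 | 96.5% v 100% | 4 | 9.2% v 97.8% | 89 |

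**Step 3: effect of the ULOQ.** SAP 5.1.1.2 sets values above ULOQ to ULOQ. The largest observable fold rise is then ULOQ divided by the Day 1 value, so a child at or above ULOQ/2.5 on Day 1 cannot exceed 2.5-fold. A cap above 2.5 x LLOQ leaves the planned rule unchanged. For the Day 1 rule at *k* = 20:

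| *U* | Responders to a 10-fold booster | Gap v inert (points) | Children above ULOQ/2.5 on Day 1 |
|---|---|---|---|
| 500 | 97% | 88 | 0.6% |
| 200 | 91% | 83 | 7% |
| 100 | 76% | 69 | 23% |
| 50 | 49% | 44 | 50% |

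**Step 4: sensitivity to *s2*.** With *s2* = 0.2 and 0.4, the planned gap at *k* = 1 is 72.4 and 61.6 points, against 89.6 and 72.4 for the Day 1 rule with *U* = 50. At *k* = 20 and *U* = 50, the planned gaps are 2.2 and 5.5, against 48.8 and 38.7. Across these cases the Day 1 rule separates better by 11-17 points at *k* = 1 and by 33-47 points in the worst capped case.

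**The case against.** The booster effect is already analysed. SAP 5.3 plans fold increases from Day 1, geometric means with intervals and Day 1 summaries, and with about 25 children per group a continuous measure keeps more information than a dichotomy. This stands: the objective is covered. However, a geometric mean fold rise can be driven by a subset, and plots drawn visit by visit do not pair a child's values, so neither gives the share of children who boosted.

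The rule is explicit, and the protocol and SAP agree on it. Response relative to the unvaccinated state is a legitimate quantity, which is a reason to keep the rate. The time points in SAP 5.3 probably include Day 1, which would show the residual share, though still not a per-child booster response.

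If the booster works well, the two rules nearly agree: at *f* = 10 without a cap, 88.6% v 87.7% at *k* = 1 and 99.9% v 97.7% at *k* = 10. That is correct, but only the Day 1 rate would attribute such a result to the booster.

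The new rate has its own bias. Under the ULOQ substitution it can badly understate a working booster where antibody has persisted at high levels (49% in the worst case above). This also stands, and is why the affected children must be counted.

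Finally, every numerical input is assumed, the adult rule is unknown, no child-adult comparison of responder rates is planned, and no passage supports 2.5-fold over Day 1 as the mark of an anamnestic response. The figures show how the rule behaves and do not predict this trial's results. The 2.5 threshold is carried over from the existing definition for consistency.

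**Conclusion.** The concern holds. Both branches of the only responder rule use the pre-dose-1 sample, and no planned proportion measures response to the booster, although the objective concerns that response and a Day 1 baseline is defined.

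The size depends on pre-booster levels that the documents do not give. Under the stated lognormal assumptions, the share counted as responders with no booster effect runs from 9-21% if antibody has fallen to about LLOQ to 89-98% at 10 x LLOQ. The problem is modest in the first case and large in the second. The study is descriptive, with no hypothesis test, sample-size basis or success criterion tied to the rate, so the consequence is confined to interpretation. The change should be made because it is cheap and supplies a quantity the plan lacks.

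**What to change.** In SAP 5.1.1.1 and 5.3, add a booster responder rate referenced to the Day 1 booster baseline. A child responds if the post-booster value is more than 2.5 times a Day 1 value above LLOQ, or above 2.5 x LLOQ when Day 1 is at or below LLOQ. Report it at Days 8 and 22 by age group with Clopper-Pearson 95% intervals, which SAP 2 already specifies. With 25 children, 25 of 25 would give 86.3% to 100%.

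Keep the existing rate, label it as relative to the pre-dose-1 sample, and state that it is also tabulated at Day 1. Beside the new rate, give the number of children whose Day 1 value is at or above ULOQ/2.5, who cannot meet the rule.

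The cost is SAP wording and one table. No extra blood is needed, because Day 1 ELISA is already scheduled for every participant, and the new rate does not depend on EBL3001 results. Its limitation is the understatement from ULOQ substitution, greatest where antibody has persisted at high levels.
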